16.2. Computerized Systems Used for Source Data

A list of the computerized systems that will be used to create, modify, maintain, archive, retrieve, or transmit source data are presented below, pursuant to the Guidance for Industry Computerized Systems Used in Clinical Investigations, May 2007.

Table 7: Computerized Systems Used for Source Data

Protocol Step	Computerized System Type or Description
Obtain informed consent	A
Obtain informed assent	A
Inclusion/Exclusion criteria	A
Randomization	A,D
Dispense study drug	A,D
Study drug accountability	A
Medical History	A
Psychiatric History	A
Prior/concomitant medication review	A
K-SADS-PL	A
Physical examination	A
Neurological examination	A
Height	A
Weight (including body mass index)	A
Vital signs	A

Table 7: Computerized Systems Used for Source Data (Continued)

Protocol Step	Computerized System Type or Description
Electrocardiogram (ECG)	C
Adverse event monitoring	A
Columbia Suicide Severity Rating Scale (C-SSRS)	A
ADHD-RS-IV HV	A
Classroom Practice Session	A
SKAMP	A
Math pretest for determination of math level	A
PERMP	A
Dosing diary distribution/review	A
Hematology/Chemistry	B
TSH	B
Serum β -hCG (in females \geq 8 years of age)	B
Urinalysis	B
Urine drug screen	A
Urine β -hCG (in females \geq 8 years of age)	A
Statistical analysis	SAS [®] , version 9 or higher

A = EDC (Medidata Rave[®]); B = LIMS; C = Core Lab Over-read; D = IXRS.

Abbreviations: ADHD-RS-IV HV = ADHD Rating Scale Version IV Home Version (modified for investigator administration), β -hCG = beta-human chorionic gonadotropin, EDC = electronic data capture; IXRS = interactive recognition system; K-SADS-PL = Schedule for Affective Disorders and Schizophrenia for School-Age Children- Present and Lifetime version, LIMS = laboratory information management system,

PERMP = Permanent Product Measure of Performance, SKAMP = Swanson, Kotkin, Agler, M-Flynn, and Pelham Scale, TSH = thyroid stimulating hormone.

16.3. Study Monitoring

This study will be monitored from initiation to completion by the Sponsor or its representative. Monitoring will include personal visits and telephone communication to assure that the investigation is conducted according to protocol and in order to comply with International Conference on Harmonization (ICH) Good Clinical Practice (GCP). On-site review of CRFs will include a review of forms for completeness and clarity, and consistency with source documents available for each subject.

16.4. Audits

The study may be subject to audit by the Sponsor/designee. If such an audit occurs, the Investigator must agree to allow access to required subject records. This is dependent on the subject granting consent/assent by signing the informed consent form (ICF)/ informed assent form (IAF). By signing this protocol, the Investigator grants permission to personnel from the Sponsor or its representatives for on-site monitoring and auditing of all appropriate study

documentation, as well as on-site review of the procedures employed in CRF generation, where clinically appropriate.

16.5. Study Documentation

Study records are comprised of source documents, CRFs, and all other administrative documents, eg, IRB correspondence, clinical study materials and supplies shipment manifests, monitoring logs, Sponsor and CRO correspondence, etc. A study specific binder will be provided with instructions for the maintenance of study records.

Source document is defined as any hand written or computer generated document that contains medical information or test results that have been collected for or are in support of the protocol specifications, eg, clinical laboratory reports, clinic notes, drug disbursement log, subject sign in sheets, subject completed questionnaires if applicable, telephone logs, ECGs, etc. All draft, preliminary and pre-final iterations of a final report are also considered to be source documents, eg, faxed laboratory reports and hard copy laboratory reports, faxed initial results and hard copy, final report.

16.6. Clinical Laboratory Certification and Normal Values

A central laboratory will be used for analysis for most of the clinical laboratory tests for this study. The central laboratory will provide the Investigator, Sponsor/CRO with laboratory certification(s), a dated copy of normal range values for the central clinical laboratory selected to analyze clinical specimens. If an exception is granted to use a local laboratory, the Investigator must supply the Sponsor/CRO with laboratory certification, lab director's curricula vitae and a current, dated copy of normal range values.

17. ETHICAL AND REGULATORY OBLIGATIONS

17.1. Study Conduct

The Investigator agrees that the study will be conducted according to the protocol, ICH Good Clinical Practice (GCP), ICH guidelines and the ethical principles that have their origin in the Declaration of Helsinki. The Investigator will conduct all aspects of the study in accordance with applicable local law(s) and regulation(s).

The Investigator will assure proper implementation and conduct of the study including those study-related duties delegated to other appropriately qualified individuals. The Investigator will assure that study staff cooperate with monitoring and audits.

The Investigator must sign and return to Sponsor/CRO the "Investigator Approval" page.

The Investigator must provide a copy of current curriculum vitae (including a copy of a current medical license, current Drug Enforcement Agency (DEA) license, where applicable), and financial disclosure information. In countries where medical licensure is not issued, the following documentation is acceptable, as applicable:

- Registration number/stamp with a registration number stated on curriculum vitae.
- Appropriate diploma number stated on curriculum vitae.
- Copy of the diploma.

The Investigator must sign and return a completed Form FDA 1572 "Statement of Investigator" to Sponsor/CRO.

17.2. Institutional Review Board

Documented approval for conducting the study from appropriate Institutional Review Board (IRB) will be obtained for all participating study centers prior to initiation of the study, according to ICH GCP, applicable local law(s) and regulation(s). When necessary, an extension, amendment or renewal of the IRB approval must be obtained and also forwarded to the Sponsor. The IRB must supply the Sponsor a list of the IRB membership, and a statement to confirm that the IRB is organized and operates according to ICH GCP, applicable law(s) and regulation(s).

A copy of written IRB approval or favorable opinion of the protocol, informed consent form and subject recruitment material (if applicable) must be provided to Sponsor/CRO prior to start of the study. The approval or favorable opinion letter must be signed by the IRB chairman or designee identify the IRB name and address, identify the clinical protocol by title and/or protocol number, and include the date that approval or favorable opinion was granted. The letter must also contain a statement that the IRB complies with the requirements in 21 CFR Part 56 for a study conducted under a US Investigational New Drug (IND) or ICH GCP, as applicable.

The Investigator/CRO is responsible for obtaining from the IRB continued review of the clinical research or submitting periodic progress reports, in accordance with applicable regulations, at intervals not to exceed one year and (if applicable) as otherwise additionally specified by the

IRB. The Sponsor must be supplied with written documentation of continued review of the clinical research.

The Investigator must promptly inform their IRB of all SAEs reported by subjects enrolled in the study or other safety information reported from Sponsor/CRO in accordance with applicable law(s) and regulation(s).

17.3. Informed Consent

The informed consent form and informed assent form will be approved by the Sponsor/CRO prior to submission to the IRB. The Sponsor/CRO may provide a template informed consent/informed assent form to be qualified by each research facility to conform to local requirements. All informed consent/assent forms must contain the minimum elements as mandated by ICH GCP, applicable local law(s) and regulations and will be subject to Sponsor/CRO approval as well as IRB approval. The Sponsor/CRO may submit informed consent forms to a central IRB for review and approval or favorable opinion contingent upon prior Investigator permission and review.

Before recruitment and enrollment, each prospective subject/parent/legal guardian will be given a full explanation of the study, allowed to read the approved informed consent form and assent form(s), as appropriate, and be provided ample time and the opportunity to ask any questions that may arise. Once all questions have been answered and the Investigator is assured that the prospective subject/parent/legal guardian understands the implications of participating in the study, the prospective subject and at least one parent/legal guardian will be asked to give consent to participate in the study by signing the informed consent and assent form(s), as appropriate. As part of the consent process, each prospective subject and at least one parent/legal guardian must consent to direct access to the subject's medical records for study-related monitoring, auditing, IRB review, and regulatory inspection. It should be clearly explained to each prospective subject/parent/legal guardian that participation in each and every clinical visit and assessment is expected. The subject may be discontinued from study medication, but that does not necessarily negate the expectation that the subject/parent/legal guardian will continue to participate in the study through the final visit/assessment. The Investigator will provide a copy of the signed informed consent form and assent forms to each subject/parent/legal guardian, and will record the date of the informed consent and assent on the CRF.

If an amendment to the protocol changes the subject participation schedule in scope or activity, or if important new information becomes available that may be relevant to the subject's parent's/legal guardian's consent/assent, the informed consent/assent form(s) must be revised, submitted to the IRB for review and approval or favorable opinion. The revised informed consent/assent form(s) must be used to obtain consent/assent from a subject currently enrolled in the study if he or she is affected by the amendment. The revised informed consent/assent form must be used to obtain consent from any new subjects who are enrolled into the study after the date of the approval or favorable opinion of the protocol amendment.

17.4. Subject Privacy

The Sponsor (or Sponsor representative) or any designees affirm uphold the subjects confidentiality. The subject will be identified by unique code only; full names will be masked

prior to transmission to the Sponsor. The confidentiality of the subject's personal data shall be protected in accordance with appropriate laws and regulations.

17.5. Protocol Amendments and Emergency Deviations

All revisions and/or amendments to this protocol must be approved in writing by the Sponsor and the appropriate IRB. The Investigator will not make any changes to the conduct of the study or the protocol without first obtaining written approval from the Sponsor and the IRB, except where necessary to eliminate an apparent immediate hazard to a study subject.

Emergency deviations or modifications may be initiated without Sponsor or IRB approval or favorable opinion, only in cases where the deviation or modification is necessary to eliminate or avoid an immediate apparent hazard to subjects. Emergency deviations or modifications must be reported to the Sponsor/CRO and the IRB immediately/within 5 business days of the occurrence, or in accordance with applicable regulatory requirements.

17.6. Records Retention

The Investigator/the study center must arrange for retention of study records at the study center for at least 15 years from time of participation in the study or longer in accordance with applicable regulations and Sponsor SOPs. The Investigator/site should take measures to prevent accidental or premature destruction of these documents. Documents cannot be destroyed without written Sponsor authorization. The Sponsor will inform the Investigator/the study center when the destruction of documents is permitted.

17.7. Inspection of Records

In the event of an inspection, the Investigator agrees to allow representatives of the Sponsor and its representative and, the regulatory authorities' access to all study records. The Investigator will promptly notify the Sponsor/CRO of all requests to inspect a Sunovion-sponsored study by government agencies and will promptly forward a copy of all such inspection reports.

17.8. Financial Disclosure

By signing this protocol, the Investigator agrees to provide to the Sponsor prior to start of study accurate financial information to allow the Sponsor to submit complete and accurate certification and disclosure statements as required by the US FDA regulations (21 CFR Part 54). The Investigator further agrees to provide this information on a Financial Disclosure/Certification Form that is provided by the Sponsor. The Investigator will update this information if there are any relevant changes during the conduct of the study and for one year after completion of the study.

The Investigator also consents to the transmission of this information to the Sponsor for these purposes. This may involve the transmission of information to countries that do not have laws protecting personal data.

17.9. Publication Policy

Any formal presentation or publication of data collected as a direct or indirect result of the study will be considered a joint publication by the Investigators and the appropriate personnel of the

Sponsor. For multicenter studies, it is mandatory that the first publication is based on all data obtained from all analyses as stipulated in the protocol. Investigators participating in multicenter studies must agree not to present data gathered individually or by a subgroup of centers before the full, initial publication, unless this has been agreed to by all other Investigators and by the Sponsor.

20. APPENDIX I. CARDIAC SAFETY MONITORING (ECG)

1. Requirements for Testing

ECG equipment and supplies will be provided by ECG Vendor and should be used for all in-clinic protocol ECG assessments.

- All 12-lead ECGs will be recorded in the same manner.
- The study center personnel must be adequately trained in performing ECGs on the specific ECG equipment used in this protocol that is provided by the cardiac safety vendor.
- To the extent possible, the same ECG machine and personnel should be used to acquire a subject's ECGs throughout the period of their participation in the study.
- ECGs will be recorded with at least one 10-second single-lead tracing recorded from Lead II.

2. Subject Restrictions and Instructions

- Prior to ECG acquisition, the subject will have rested 5 minutes in the supine position and will remain so until the ECG is obtained.

3. Reporting

- It is the responsibility of the Investigator to perform a safety review of the ECG data for changes from previous assessments and/or emergent cardiac dysfunction, and to determine subjects' eligibility or continuance in the study.
- ECGs will be reviewed, signed and dated by the Investigator listed on the Form FDA 1572 (MD or DO) after each ECG collection. The same Investigator should review all ECG reports for a given subject whenever possible.
- For all ECGs, a report will be provided by the cardiac safety vendor to the study center for review and signature.
- The ECG tracing will be kept with subject's source documentation and / or CRF unless it is specified otherwise. The original ECG and the cardiologist's over-read will be retained at the study center.

4. Data Standardization

ECG data will be transmitted to a centralized cardiac safety vendor and centrally over-read and interpreted using standardized procedures.

21. APPENDIX II. BODY MASS INDEX DETERMINATION

Body mass index (BMI) will be calculated by measuring the subject's height and weight (both determined without subject wearing shoes) and using these measurements (in centimeters and kilograms) in the following formula.

Formula:

$$BMI = weight (kg) \div [height (m) \times height (m)]$$

BMI will be automatically calculated at screening by EDC, and not by the site staff.

22. APPENDIX III. CLINICAL LABORATORY TESTS

The following clinical laboratory tests are to be performed.

Clinical Safety Panel

HEMATOLOGY: (Differential reported as % and absolute value)
Hemoglobin, Hematocrit, Platelet Count, RBC Count, WBC - Total Count, WBC Differential, (Basophils, Eosinophils, Lymphocytes, Monocytes, Neutrophils)

BLOOD CHEMISTRIES: Alanine aminotransferase (ALT), Alkaline Phosphatase (ALP), Aspartate aminotransferase (AST), Bicarbonate (HCO₃), Bilirubin (Total, Direct, Indirect), Blood Urea Nitrogen (BUN), Calcium (Ca), Chloride (Cl), Creatinine, Glucose, Magnesium (Mg), Phosphorus (P), Potassium (K), Protein (Total), Sodium (Na), Uric Acid, Albumin

URINALYSIS: Blood, Glucose, Ketones, Leukocyte esterase, Microscopic examination, Nitrites, pH, Protein

THYROID PANEL: Thyroid stimulating hormone (TSH)

URINE DRUG SCREENING: Amphetamines, Barbiturates, Benzodiazepines, Cannabinoids, Cocaine, Cotinine, Methamphetamines, Methadone, Methylenedioxymethamphetamine (MDMA), Phencyclidine (PCP), Opiates, Oxycodone

OTHER TESTS: Serum Pregnancy (β -HcG) (in female subjects only ≥ 8 years of age), Urine Pregnancy Test (in female subjects only ≥ 8 years of age)

Laboratory reports will be initialed and dated on all pages by the Investigator listed on the Form FDA 1572 (MD or DO). Laboratory test results will be reviewed by the Investigator as they become available. The Investigator must determine the clinical significance of all out-of-range lab values (except drug screens). Possibly drug-related or clinically relevant abnormal values of uncertain causality must be repeated. Any abnormal values that persist should be followed at the discretion of the Investigator.

[figure not shown]
23. APPENDIX IV. CLINICALLY RELEVANT CYP2B6 SUBSTRATES OR INDUCERS OR INHIBITORS (GENERIC NAMES)

The following drugs are prohibited during this study.

Substrate	Inhibitor	Inducer
artemisinin	clopidogrel	artemisinin
bupropion	thiotepa	carbamazepine
cyclophosphamide	ticlopidine	efavirenz
efavirenz	voriconazole	nevirapine
ifosfamide		phenobarbital
Ketamine		phenytoin
meperidine		rifampin
methadone		
nevirapine		
Propafol		
Selegiline		
sorafenib		

Flockhart DA. Drug Interactions: Cytochrome P450 Drug Interaction Table. Indiana University School of Medicine (2007). <http://medicine.iupui.edu/clinpharm/ddis/table.aspx>. Accessed 4 March 2016.

24. APPENDIX V. GROWTH CHART (MALE).

[figure not shown]

25. APPENDIX VI. GROWTH CHART (FEMALE).

2 to 20 years: Girls
Stature-for-age and Weight-for-age percentiles

NAME _____

RECORD # _____

Published May 30, 2000 (modified 11/21/00).
SOURCE: Developed by the National Center for Health Statistics in collaboration with
the National Center for Chronic Disease Prevention and Health Promotion (2000).
<http://www.cdc.gov/growthcharts>

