Selected Concomitant Medications: Subject must not have taken any of the following medications: anticonvulsants for seizure control within 2 years prior to screening; antipsychotic medication within 6 months prior to screening; herbal and/or complementary treatments, e.g., St. John's Wort, or antidepressant medications (e.g., bupropion, serotonin norepinephrine reuptake inhibitor [SSRI]/selective serotonin reuptake inhibitor [SNRI], tricyclic, etc.) within 6 months prior to Day 1, monoamine oxidase (MAO) inhibitors at any time, or non-stimulant product as treatment for ADHD within 4 weeks prior to the start of screening.

Any subjects receiving stimulant medication for ADHD will discontinue that ADHD treatment for

3 - 5 days prior to Day -1 in order to ensure that there is at least a 72-hour washout before the assessment of ADHD symptoms on Day -1. Treatment with any ADHD medication is prohibited during the washout period. In addition, all subjects are required to refrain from other prohibited medications for at least 7 days, unless otherwise specified, prior to the first dose of study drug.

Use of any of the following medications is not permitted during the study from screening through the EOS visit: lithium; alpha-2 adrenergic receptor agonists (including clonidine and guanfacine), modafinil, armodafinil, atomoxetine, or any stimulant class agent (methylphenidate- or amphetamine-based); antidepressant medications (e.g., bupropion, SSRI/SNRI, MAO inhibitor, tricyclic, etc.); anticonvulsant medications (e.g., phenytoin, carbamazepine, lamotrigine, valproic acid, etc.); antipsychotic medications; pseudoephedrine-containing medications; medications with significant effect on blood pressure or heart rate (intermittent use of asthma treatments is permitted but should be discussed with the medical monitor); sleep aids (with the exception of melatonin); diphenhydramine except topical formulations; herbal and/or complementary treatments, e.g., St. John's Wort; or CYP2B6 substrates or inhibitors or inducers of CYP2B6. Subjects who require persistent asthma treatment during the study should be discussed with the medical monitor as they may be required to be discontinued from the study.

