8.1. Subject Inclusion Criteria

The subjects who fulfill the following criteria will be included in the study.

1. Subject is 6 - 12 years old, inclusive at screening and randomization.
2. Subject weighs ≤ 30 kg at the time of screening.
3. At least one of the subject's parents/legal guardians must give written informed consent, including privacy authorization, prior to study participation. The subject will provide informed assent prior to study participation.
4. Subject meets Diagnostic and Statistical Manual of Mental Disorders Fifth Edition (DSM-5) criteria for a primary diagnosis of ADHD (inattentive, hyperactive, or combined presentation) at screening established by a comprehensive psychiatric evaluation that reviews DSM-5 criteria and confirmed using the Schedule for Affective Disorders and Schizophrenia for School-Age Children-Present and Lifetime version (K-SADS-PL) at screening.
5. Subject is currently either untreated for ADHD or receiving a treatment regimen of a stimulant medication prescribed as monotherapy (i.e., methylphenidate, mixed amphetamine salts, lisdexamphetamine, or dextroamphetamine) within the approved labeled dose range for ADHD.
6. In the opinion of the investigator, the subject is not treatment refractory.
7. Any subject not receiving ADHD medication at screening must display clinically significant ADHD symptoms, as measured by an ADHD-RS-IV score ≥ 26 at screening and Day -7.
8. For any subject receiving monotherapy stimulant treatment for ADHD, that treatment must be well tolerated and clinically effective based on clinical assessment and informant interview, as well as, review of available medical records. Note: The ADHD Rating Scale Version IV - Home Version (modified for investigator administration) (ADHD-RS-IV HV) will be administered at Screening by the investigator to inform clinical evaluation.
9. Subject is male or a non-pregnant, non-lactating female.
10. Subject, if female, must not be pregnant or breastfeeding, and if ≥ 8 years of age must have a negative serum pregnancy test at screening.

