10.3.1. Prohibited Medications

Subject must not have taken any of the following medications within the timeframe listed:

- Anticonvulsants for seizure control within 2 years prior to screening
- Antipsychotic medication within 6 months prior to screening
- Herbal or complementary treatments, eg, St. John's Wort, within 6 months prior to Day 1
- Any antidepressant medication (eg, bupropion, SSRI/ SNRI, tricyclic, etc) within 6 months prior to Day 1
- MAO inhibitor at any time
- Non-stimulant product as treatment for ADHD within 4 weeks prior to the start of screening.

Any subjects receiving stimulant medication for ADHD will discontinue that ADHD treatment for 3 - 5 days prior to Day -1 in order to ensure that there is at least a 72-hour washout before the assessment of ADHD symptoms on Day -1. Treatment with any ADHD medication is prohibited during the washout period. In addition, all subjects are required to refrain from other prohibited medications for at least 7 days, unless otherwise specified, prior to the first dose of study drug.

Use of any of the following medications is not permitted during the study from screening through the EOS visit:

- Lithium (any lithium preparation or formulation)
- Alpha-2 adrenergic receptor agonists (including clonidine and guanfacine), modafinil, armodafinil, atomoxetine, or any non-stimulant class agent
- Antidepressant medications (eg, bupropion, SSRI/SNRI, MAO inhibitor, tricyclic, etc)
- Anticonvulsant medications (eg, phenytoin, carbamazepine, lamotrigine, valproic acid, etc) and antipsychotic medications
- Pseudoephedrine-containing medications
- Medications with significant effect on blood pressure or heart rate. Intermittent use of asthma treatments is permitted but should be discussed with the medical monitor.
- Sleep aids with the exception of melatonin
- Diphenhydramine except topical formulations
- Herbal or complementary treatments, eg, St. John's Wort
- CYP2B6 substrates or inhibitors or inducers of CYP2B6 (see [Section 23](#), Appendix IV).

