11.5.2.2. Visit 5 (Day 15): Second Laboratory Classroom Day

At this visit the subject should arrive at the clinic by 6:30 AM and the following study-related procedures will be performed:

- Perform study drug accountability
- Collect dosing diary
- Record prior and concomitant medications
- Record AEs
- Measure weight, record BMI
- Collect vital signs once. For each subject the time should be the same as on Day 1.
- Administer C-SSRS since last visit version
- Collect samples for UDS, urine pregnancy test for females ≥ 8 years of age
- Conduct 7 classroom sessions according to the Laboratory Classroom Manual.

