#### 4.5 Protocol Deviations

Protocol deviations (PDs) will be collected during monitoring visits. Protocol deviations will be placed into, but not limited to, the following categories: prohibited concomitant medications, dosing, enrollment inclusion/exclusion criteria, laboratory, non-compliance, and others which are deemed to be study PDs. Each instance of a PD will be reviewed and determined to be important or minor before the study DBL.

A summary of important PDs will be provided as number (%) of subjects with at least 1 important PD and number (%) of subjects in each category in all randomized subjects. A listing by subject will also be provided that will include all PDs, deviation date, type, and any specific comments related to the deviation.

The following conditions, if met, would constitute an important PD. As such, any subject meeting one or more of these conditions would be omitted from the PP population. Important PDs are not limited to the list below. All protocol deviations within the monitoring report and the clinical database will be reconciled and adjudicated by the clinical team after the study is complete for the identification of all other important PDs.

	Category	Explanation
1	No proof of randomization or subjects mistakenly randomized	At Visit 4, there is no randomization number indicated on CRF field or subject mistakenly assigned randomization number.
2	Subject is non-compliant	Subject is not lost to follow-up and is <75% or >125% compliant with study drug.
3	Prohibited medications taken	Subject took any of the prohibited medications listed in Section 10.3.1 of the protocol during the study from screening through the EOS visit, unless the medication is clinically adjudicated as permissible.

4	Treated subject who did not meet inclusion/exclusion criteria	Subject failed one or more of the inclusion or exclusion criteria listed in Section 8 of the protocol, but continued in the double-blind period of the study.
5	Subject tests positive for substance abuse	Subject has one or more positive urine drug screen test at any visit during the course of the study.
6	Subject is unblinded during study	Subject is unblinded to treatment at any time during the course of the study.
7	Subject receives incorrect treatment	Subject's actual treatment received does not match randomized planned treatment.
8	Subject misses Day 15 visit	Subject is randomized and receives treatment, but is not present for the Day 15 classroom assessments

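### The urine drug screen has no methylphenidate test, so on the classroom days it can detect only amphetamine-type ADHD stimulants, and per-protocol membership depends on which stimulant a child took

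*Protocol*

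**What the plan says.** - **Panel.** Protocol Appendix III: "URINE DRUG SCREENING: Amphetamines, Barbiturates, Benzodiazepines, Cannabinoids, Cocaine, Cotinine, Methamphetamines, Methadone, Methylenedioxymethamphetamine (MDMA), Phencyclidine (PCP), Opiates, Oxycodone". That is 12 items, none of them methylphenidate.
- **Prior treatment.** Protocol 8.1, criterion 5, admits untreated children and children on "a stimulant medication prescribed as monotherapy (i.e., methylphenidate, mixed amphetamine salts, lisdexamphetamine, or dextroamphetamine"). Criterion 8 requires the existing stimulant to be tolerated and effective.
- **On-study prohibition.** From screening to the end-of-study (EOS) visit, the synopsis bars "any stimulant class agent (methylphenidate- or amphetamine-based"). The corresponding list in Protocol 10.3.1 reads "modafinil, armodafinil, atomoxetine, or any non-stimulant class agent".
- **Sampling.** The schedule of assessments has a urine drug screen at screening, Day 1, Day 15 and EOS. For the second classroom day, Protocol 11.5.2.2 says: "Collect samples for UDS, urine pregnancy test for females ≥ 8 years of age".
- **PP rules.** SAP 4.5 rule 5 counts as an important deviation: "Subject has one or more positive urine drug screen test at any visit during the course of the study". Rule 3 counts prohibited medication, as listed in Protocol 10.3.1. SAP 4.3 describes PP as a supplemental population for judging robustness.

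**The concern.** The trial enrols children whose symptoms are controlled on a stimulant, withdraws it, and assigns half of those randomized to placebo for 14 days. A stimulant given before a classroom day could affect the SKAMP score directly. On Day 1 that would disturb the baseline, and on Day 15 the outcome. Urine is collected on exactly those two days, but the panel covers only one of the two stimulant classes that the synopsis names.

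The consequence for the PP analysis is uneven treatment of like cases. A child given an undeclared amphetamine product can be detected and removed. A child given undeclared methylphenidate stays in unless the family discloses it. A robustness analysis should not depend on which of two equally prohibited drugs was taken.

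**Working it through.** **1. Panel against permitted stimulants.** Criterion 5 names four.

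| Permitted prior stimulant | Item on the Appendix III panel |
|---|---|
| Methylphenidate | none |
| Mixed amphetamine salts | amphetamines |
| Lisdexamphetamine | amphetamines |
| Dextroamphetamine | amphetamines |

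The matching is by drug class as named. The documents do not say whether any listed assay reacts to methylphenidate, so the point rests on the list as written.

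**2. Other routes to detection.** The medication review at each visit and the Day -1 telephone contact both depend on what the family says. SAP rule 3 works only if the use is known. It also points to Protocol 10.3.1, whose on-study list, read literally, does not name stimulants; that section's ban on all ADHD medication is tied to the washout period. The synopsis does name stimulants, so the two passages contradict each other.

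**3. Rule 5 at screening.** The rule covers every visit, and a screen is taken at Visit 1, when a child may properly be on a permitted stimulant. The note to exclusion 30 lets a child continue if a positive is explained by prescribed medication. That note settles eligibility, not PP membership. As written, an amphetamine-treated child with an explained screening positive leaves PP, and a methylphenidate-treated child does not.

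**4. The plan's sample size.** Inputs from Protocol 15.1: d = 0.7, two-sided alpha 0.05, two-sample t-test, 44 per group. Noncentrality is 0.7 × √(44/2) = 3.28 on 86 degrees of freedom, giving power 0.901. With 43 per group it is 0.894, so 44 is confirmed. Allowing for dropout, 88/(1 − 0.12) = 100. The plan's figures reproduce, and the panel does not enter them.

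**5. Scale of undetected use (illustration).** Suppose a share q = k/44 of one arm takes methylphenidate on Day 15, with effect e in SD units. The documents give neither q nor e. The range 0.70 to 0.95 is borrowed from the dasotraline effect sizes in Protocol 15.1.

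For placebo-only use, the difference is 0.7 − q·e, the placebo variance is 1 + q(1 − q)e², and the pooled SD is the square root of the mean of 1 and that variance. Example for k = 2, e = 0.70: q = 0.0455, difference 0.668, pooled SD 1.005, standardized effect 0.665, power 0.869. With equal use in both arms, the difference stays at 0.7 and only the variance rises.

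| Users per affected arm | e | Power, placebo only | Power, both arms |
|---|---|---|---|
| 2 of 44 | 0.70 | 0.869 | 0.895 |
| 2 of 44 | 0.95 | 0.855 | 0.890 |
| 4 of 44 | 0.70 | 0.832 | 0.889 |
| 4 of 44 | 0.95 | 0.798 | 0.879 |

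Most of the loss comes from assuming that only placebo children resume.

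**The case against.** The strongest reply is that this is a substance-abuse screen, not a washout check. Exclusion 30 sets it beside alcohol and nicotine, SAP rule 5 is titled in terms of substance abuse, and cocaine, opiates and cotinine fit that purpose. Stimulant use is handled by medication review and rule 3. There are safeguards too: parents are told to keep other ADHD treatments out of the child's reach (Protocol 9.3), sites attempt daily contact (10.2), and a Day -1 ADHD-RS-IV score of at least 26 is required.

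The statement of purpose is fair, but rule 5 still removes amphetamine positives from PP, whatever the screen is called. The safeguards make covert dosing less likely. They all run through the caregiver, and the Day -1 score says nothing about a dose given on Day 1 or Day 15.

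A reader might infer three stronger things:

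- **That the primary analysis loses 3 to 10 points of power and a wider panel restores it.** The documents give no frequency of use and no methylphenidate effect on SKAMP. The ITT analysis has no urine-screen rule, so detection alone would recover none of that loss.
- **That the omission favours one arm.** The imbalance shown is between stimulant classes. Whether resumed use would differ by arm in a blinded trial is not known.
- **That adding the analyte is enough.** With rule 5 unchanged, methylphenidate-treated children who test positive at screening would also be dropped from PP.

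**Conclusion.** The point holds in a limited form. The panel tests for one of the two stimulant classes permitted before entry and barred by the synopsis, so the plan has no objective check of methylphenidate washout or resumed use on the classroom days. PP membership under rule 5 depends on the class of drug taken. That weakens a supplemental robustness analysis and leaves a possible distortion of classroom scores unobserved.

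It does not make any stated sample size, power or alpha wrong. The power figures of 0.87 to 0.80 assume placebo-only use, 2 to 4 users among 44, and an effect borrowed from dasotraline. With equal use in both arms, power stays at 0.88 to 0.89. The change is worth making because the urine is already collected and the correction is small.

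**What to change.** 1. **Appendix III:** add methylphenidate or its urinary metabolite to the screen for the Day 1 and Day 15 samples.
2. **SAP 4.5 rule 5:** for stimulants, count a Day 1 or Day 15 positive for either class as an important deviation. Do not count a screening positive explained by a permitted prescribed stimulant. The handling of the other analytes need not change.
3. **Protocol synopsis and 10.3.1:** reconcile the two on-study lists, because SAP rule 3 relies on 10.3.1.

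The cost is 100 children × 2 days = about 200 assays, with no new visit or collection and no change to N, alpha or the primary model. Protocol Table 7 records the drug screen in EDC rather than in the laboratory system, and 11.4.2 allows point-of-care kits. The screen may therefore be an on-site kit, in which case a separate strip or a central sample would be needed. A central Day 1 result could arrive after randomization and would then serve PP classification only. The documents give no detection window for any analyte, so the laboratory should confirm that a completed washout would not itself read positive on Day 1.
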